5.1.5 Criteria for clinical trial suspension or termination

When the incidence of grade 3 and above adverse reactions reaches 15% or above or a case of suspected and unexpected serious adverse reactions (SUSAR) occurs, the sponsor,

investigator, and ethics committee shall discuss whether there is a need to suspend or terminate the clinical trial.

6. Study Treatments

At present, there is no Inactivated SARS-CoV-2 vaccine on the market. In order to ensure the scientific evaluation of the vaccine, considering that the final product of this vaccine contains adjuvant, aluminum hydroxide adjuvant with the same dose is selected as placebo control.

6.1. Study Products Description and Characteristics

The inactivated SARS-CoV-2 vaccines (Vero cell) are prepared by inoculating African green monkey kidney cells (Vero cell) with the SARS-CoV-2 WIV04/HB02 strain, culturing, harvesting, inactivating, clarifying, concentrating, purifying and adding aluminum hydroxide adjuvant. After inoculating the vaccine, the recipients can produce immune response against diseases caused by SARS-CoV-2.

6.1.1. Investigational vaccine-1

Name: Inactivated SARS-CoV-2 vaccine (Vero cell)

Manufacturer: Wuhan Institute of Biological Products Co., Ltd.

Wuhan Institute of Virology, Chinese Academy of Sciences

Specification: 200 WU/dose for each person, 0.5 mL for each dose

Storage conditions: 2-8 °C

Batch Number of Vaccine: 202006009/202006011

See "Specification Report" of National Institute for Food and Drug Control

6.1.2. Investigational Vaccine-2

Name: Inactivated SARS-CoV-2 vaccine (Vero cell)

Manufacturer: Beijing Institute of Biological Products Co., Ltd.

Specification: 0.5 ml/dose per person, containing 4µg of viral protein

Storage conditions: 2-8 °C

Batch Number of Vaccine:202005003

See "Specification Report" of National Institute for Food and Drug Control

6.1.3. Placebo control

Name: Inactivated SARS-CoV-2 Vaccine (Vero Cell) Aluminum Adjuvant

Manufacturer: Wuhan Institute of Biological Products Co., Ltd.

Storage conditions: 2-8 °C

Specification: 0.5 mL for human use every time, without SARS-CoV-2 antigen.

Batch Number and Validity Period: 202006002

See the Specification Report by National Institute for Food and Drug Control.

6.1.4. Production Technology

The preparation of this SARS-CoV-2 vaccine is done by inoculating the isolated and qualified SARS-CoV-2 strain on Vero cells. After culturing the cells, harvesting the virus solution, concentrating, inactivating with β -propiolactone, purifying, and adsorbing with aluminum hydroxide adjuvant, the vaccine is fully prepared. The vaccine production process adopts culture technology to obtain high titer virus harvest solution. After ultrafiltration concentration and column chromatography purification, the virus purified solution with a purity of more than 95% was obtained. After virus inactivation, the monovalent stock solution was prepared, and after adjuvant adsorption, the product was packaged into a finished product. All quality parameters fully met the requirements of "Regulations for Manufacturing and Vero Cell of SARS-CoV-2 Inactivated Vaccine".

- ✓ The whole batch inactivation method is adopted to ensure the inactivation effect, uniformity and immunogenicity of the virus.
- ✓ Chromatography purification process is adopted to improve the purity and safety of the product. Large volume chromatography column is adopted to ensure the uniformity of product quality.

6.2. Non-investigational Medicinal Products

There are no non-investigational medicinal products in this study.

6.3. Blinding Procedures

6.3.1. Methods of blinding and Randomization

Statistical staff for allocation of concealment would write the programs for random grouping and make the blind codes. Blind codes are divided into primary blind codes and secondary blind codes. , Blind codes will be stored in a restricted location with access granted only to the unblinded statistical staff. The primary blind codes are the group codes, and each vaccine number is the investigational vaccine or control vaccine corresponding to the research number, which is represented by different letters. The secondary blind codes will uncover the final blind codes, i.e. the vaccine name represented by letters, and the low-dose, medium-dose and high-dose investigational vaccine or control vaccine. The random grouping allocate in concealment program and blind codes are put into envelopes in duplicate, signed and sealed, and kept in one copy for the investigator and one copy for the sponsor respectively. Staff for allocation of concealment are not allowed to participate in clinical trials, nor are they allowed to disclose any content regarding the allocation of concealment to any staff participating in clinical trials.

The sponsor shall provide the qualified investigational vaccines and control vaccines, and the third-party statistical unit shall organize the allocation of concealment. Stata 12.0 software shall be used to generate random codes by randomization method, and the investigational vaccines and control vaccines shall be randomly allocated with serial numbers (each vaccine has a unique serial number).

6.3.2. Code breaking during the study

(1) Unblinding

When the immunogenicity results for 14 days after the whole course of immunization are obtained, adequate confirmed cases of COVID-19 are collected, the database is locked and unblinded after ensuring that the data are correct, and the safety, immunogenicity and protection effect will be evaluated after unblinding.

(2) Emergency Unblinding

If there is an emergency (such as serious adverse events) in the field work, inform the Ethics Committee and carry out emergency unblinding if necessary.

An online electronic system will be used for emergency unblinding. An investigator will be authorized in the research site, usually the person in charge of the site. When an emergency unblinding occurs in the research site, such as SAEs potentially associated with vaccines, quick knowledge of vaccine groupings is needed, in order to carry out emergency treatment. On-site investigators can log in to their personal authorized account number on the system to initiate an emergency unblinding application. The system will send the emergency unblinding application to the sponsor, PI and monitor simultaneously for approval. After all authorized personnel log in to the system and approved, the online system will inform the on-site person the blind codes of the research number. In case of clustered adverse events or interruption of the trial for any reason, the sponsor and the investigator shall jointly approve for unblinding in advance.

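### Emergency code release waits for approval by the sponsor, the PI and the monitor, so any one of them can delay or block information the protocol says is needed quickly

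*Protocol*

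**What the plan says.** Section 6.3.2(2) of the Protocol sets out emergency unblinding as follows.

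- **Purpose.** For events such as SAEs possibly linked to the vaccine, "quick knowledge of vaccine groupings is needed, in order to carry out emergency treatment".
- **Route.** "An online electronic system will be used for emergency unblinding".
- **What the site may do.** "On-site investigators can log in to their personal authorized account number on the system to initiate an emergency unblinding application". One investigator per site is authorised, usually the person in charge there.
- **Who decides.** "The system will send the emergency unblinding application to the sponsor, PI and monitor simultaneously for approval".
- **When the code is released.** "After all authorized personnel log in to the system and approved, the online system will inform the on-site person the blind codes".
- **Ethics committee.** The opening sentence says to "inform the Ethics Committee and carry out emergency unblinding if necessary".

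A separate sentence requires joint sponsor and investigator approval to unblind early for clustered adverse events or interruption of the trial.

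Section 6.3.1 covers custody of the codes. It says "Blind codes will be stored in a restricted location with access granted only to the unblinded statistical staff", and also that duplicate envelopes are "signed and sealed, and kept in one copy for the investigator and one copy for the sponsor respectively".

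**The concern.** The purpose and the mechanism sit in the same paragraph and pull against each other. The purpose is speed for the treating site. The mechanism makes release depend on three approvals, two of them from parties with no role in treating the subject. Sections 10.2 and 11.4 describe monitoring as progress review, case report form checks and source data verification. The sponsor's role here is likewise one of oversight.

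What is at stake is timely access to one subject's allocation when the protocol itself says it bears on care. Section 8.2(4) makes the same link: once unblinded, membership of the experimental group informs the assessment of possible ADE or VED in rapidly progressing disease, and the advice given to doctors. No view is taken here on that clinical advice. The rule also gives the sponsor and the monitor an effective veto over a request raised by the site for treatment.

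**Working it through.** The protocol states no figure on this point, so there is nothing to reproduce. The check is a reading of the relevant sections side by side.

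1. **Structure of the release rule (6.3.2(2)).** Requests go out in parallel, so the approvals do not add up one after another. Reading the phrase about all authorised personnel as the three parties named in the preceding sentence, the waiting time is max(t_sponsor, t_PI, t_monitor). If any one party refuses or does not respond, no code is released under the text as written.

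2. **Safeguards on that time.** The section gives no maximum response time, no default on non-response, no deputy or on-call cover, and no power for the investigator to release the code alone. The waiting time therefore has no stated upper limit.

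3. **Other routes in the protocol.**
   - *Sealed envelopes (6.3.1).* One copy is kept for the investigator. The section does not call it an emergency route, and it also confines code access to unblinded statistical staff. Section 6.3.2(2) names the online system as the means. The envelope is not a usable fallback until these statements are reconciled.
   - *DSMB request (8.5).* The DSMB may ask for an individual's arm for safety assessment. That serves board review and gives the treating site no access.
   - *Ethics committee (6.3.2(2)).* It is to be informed. Its approval is not required, and the system steps that follow do not mention it, so it is not a release condition.

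4. **Comparison with backup vaccine (6.4.2).**

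| | Backup vaccine (6.4.2) | Emergency code (6.3.2(2)) |
|---|---|---|
| System | Online | Online |
| Who applies | Site staff | Site's authorised investigator |
| Whose approval releases | Person in charge on site | Sponsor, PI and monitor, all of them |
| Role of sponsor, PI and monitor | Notified at the same time | Must approve first |

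The person in charge on site can release a replacement dose on their own approval. The same person, as the usual unblinding investigator, cannot obtain one subject's allocation in an emergency. The less urgent action has the faster rule.

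**The case against.** Five points can be made for the plan as written.

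- **Parallel requests.** They go out together through a system built for the purpose, and no turnaround time is stated. A reader might infer that the rule makes emergency unblinding useless. The documents do not show that: approvals could come within minutes. They support only that release can be delayed or blocked.
- **Care is not conditional on the code.** Section 8.3 tells investigators to act immediately on serious adverse events, and section 8.1 puts emergency staff and an ambulance on standby during vaccination. A reader might infer that treatment is withheld pending approval. It is not; only knowledge of the arm is.
- **The PI may be local.** The text does not say whether the PI is also the site's authorised investigator. If so, two outside approvals remain instead of three. That reduces the problem without removing it.
- **The ethics committee.** A reader might count it as a fourth gate. The wording supports notification only.
- **Material not shown.** Site emergency plans and SOPs under section 8.3 might provide approver cover. That is possible, but such documents would still have to work within a protocol rule that requires every approval.

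The first four limit how strongly the point can be put. None removes the all-must-approve condition or its conflict with the stated need for speed.

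**Conclusion.** The point holds in this form: section 6.3.2(2) makes emergency release depend on every one of three approvers, with no time limit, default or override, although the same paragraph says the arm is needed quickly for treatment. Any one approver can delay or block release. The envelopes in section 6.3.1 and the DSMB request in section 8.5 do not repair this.

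The size is qualitative. The expected delay and the share of emergencies affected cannot be estimated, because the protocol gives no response times or cover arrangements, and any percentage would rest entirely on assumed inputs. The conclusion rests on two readings: that all authorised personnel means the sponsor, the PI and the monitor, and that the envelopes are not an emergency route because the protocol does not say they are. The point concerns subject safety and site authority; it does not affect the efficacy analysis. It should be corrected.

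**What to change.** Amend section 6.3.2(2) as follows.

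- Let the site's authorised investigator obtain the single subject's code from the online system on entering the reason.
- Replace the three prior approvals with same-time notice to the sponsor, the PI and the monitor that a code was broken, without disclosing the arm, and require a documented justification afterwards. This carries over the pattern of section 6.4.2.
- State that informing the ethics committee does not hold up release.
- Keep joint sponsor and investigator approval for clustered events or trial interruption.

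Reconcile section 6.3.1 with this: say who holds the codes, who may open them, and whether the investigator's envelope is a fallback if the system is down.

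The cost is about a paragraph of protocol text and a change to release permissions. The protocol does not describe how the unblinding system is configured, so the technical effort is not known. The audit trail in section 11.1 is described for electronic data capture, so logging of code breaks should be stated for the unblinding system as well. The downside is that a few more individual code breaks may occur. Restricting release to one subject at a time, recording the reason and withholding the arm from those notified keep that loss of blinding small.

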6.4. Vaccine packaging and labelling

All investigational vaccines are packaged in different doses in boxes with the same appearance and only marked by the random number of vaccines. The random number of vaccines is the research number. Different vaccine doses under the same research number are distinguished by the suffix of the random number. The numbering rules are as follows: XXXXX-1 represents the first dose of vaccine for XXXXX subjects, XXXXX-2 represents the second dose of vaccine for XXXXX subjects,

6.4.1. Vaccine labeling

(1) Each vaccine 0.5 ml dose shall be packaged separately in a single dose syringe, and the vaccine number shall be stucked.

(2) After the vaccine is put into use, the initials of the subject and the vaccination date shall be filled in the outer package respectively, and the active tag shall be stucked onto the original record form. The vaccination staff shall verify before conducting vaccination. During the trial process, the outer package of all used vaccines shall be kept for future reference.

Vaccines, small boxes are distinguished by different vaccine doses under the same research number, i.e. Random number and suffix.

Phase III Clinical Trial Label Illustration

(1) Outer packing box label:

SARS-CoV-2 Vaccine (Vero Cell), Inactivated		
Only used for clinical trial		
Vaccine number: XXXXXX		
Initials:	Immunization date: MM DD YY	
Store at 2-8 °C, 0.5 mL/dose		
Batch Number: 202005003/202006009/202006002		
Valid until: May 8, 2022		

(2) Vaccine syringe:

SARS-CoV-2 Vaccine (Vero Cell), Inactivated	
(Only for Clinical Trial)	
Vaccine Number: XXXXXX	
Batch Number: 202005003/202006009/202006002	

SARS-CoV-2 Vaccine (Vero Cell), Inactivated		
Only used for clinical trial		
Vaccine number: XXXXXX		
Initials:	Immunization date: MM DD YY	
Store at 2-8 °C, 0.5 mL/dose		
Batch Number: 202005003/202006009/202006002		
Valid until: May 8, 2022		

(3) Movable Label:

Vaccine No.: XXXXXX

Initials:

Vaccine No.: XXXXXX

Initials:

6.4.2. Backup vaccine

In case of vaccine damage (including package damage), unstable sediment, abnormal turbidity, etc. cannot be used (determined according to dosage form), backup vaccines must be put into use and 2% backup vaccines must be prepared for each dose. Using an online electronic system to obtain the number of the backup vaccine, once the vaccination staff or vaccine administrators on the research site identify an abnormal situation of the vaccine, vaccination should be suspended immediately, and an application for access to backup vaccines should be initiated through the online system. After the approval by the person in charge on site, the vaccine administrator and vaccination staff should pick the backup vaccines with relevant numbers from the stock for vaccination. The access to backup vaccines would be sent to the sponsor, PI and monitor by the system at the same time. When the backup vaccine is put into use, its label and the original vaccine label should be stuck onto the original record at the same time.

6.5. Products Storage and Stability Procedures

Vaccines should be stored and transported at 2 ~ 8 °C away from light to prevent freezing. The temperature during vaccine transportation and storage shall be dynamically monitored and recorded. If the storage and transportation temperature conditions exceed the specified range, the on-site investigators should immediately contact the personnel of the responsible clinical institutions and the sponsors to decide whether the vaccine can be used.

The responsible institution for vaccine clinical trials shall guide the site to formulate a management system for the investigational vaccine, and the management of receiving, keeping, preparing, recovering, returning/destroying of the investigational vaccine shall conform to the requirements of relevant laws and regulations. The responsible institution for vaccine clinical trials and the site shall designate personnel who have received GCP and relevant training to be responsible for the management of vaccines for trials.

6.5.1. Vaccine transportation

The whole process of vaccine management should meet the requirements of the cold chain, and there should be vaccine transportation and storage conditions that meet the requirements of the protocol. During the transportation of vaccines, there should be a transportation sheet and temperature monitoring. Upon arrival, the packaging condition and unpacking temperature should

be recorded. After the receiver receives the vaccines, the transportation sheet should be signed, faxed or copied to the consignor. Both parties should properly keep the transportation sheet.

6.5.2. Vaccine storage, distribution and use

Vaccines for testing should be kept in a separate area, locked in dedicated closet and managed by dedicated personnel. Vaccine receiver must verify and record the batch number, expiration period and delivery status of vaccines, establish work forms for vaccine handover, registration, use and recovery, fill in them as required, and keep them in the work records.

Investigational vaccine shall not be used for those are not clinical trial subjects.

6.5.3. Vaccine records

The sponsor will provide investigational vaccine, control vaccine (placebo) and vaccine handover sheet, and investigator will verify the name, batch number and quantity of the vaccine while receiving the vaccine.

Vaccine registration and use records: investigator shall establish vaccine registration and use records and distribute investigational vaccine and control vaccines according to the number of observation groups.

Record of vaccine recovery: The abandoned, expired and the remaining vaccines in this trial are returned to sponsor. Sponsor receives vaccines and verifies the batch number and quantity of vaccines, fills in the vaccine handover form, and makes relevant records, which are signed by vaccine manager and sponsor representatives.

6.6. Administration Route and Immunization Procedure

Administration route: lateral deltoid muscle of upper arm, intramuscular injection.

Immunization procedure: The subjects will complete 2 doses of vaccine on D0, D21(+7) days.

7. Study Schedule of Events and Visit Descriptions

7.1. Schedule of Events

Study assessments and procedures are presented by study period and visit in Table 4.

For all visits after the randomization visit, if the visit 2 is changed, then the next visit should take place according to the original study schedule.

7.2. Study Visit Descriptions

7.2.1. Procedures Performed at the Screening/Baseline Visit(s) D0

The following procedures/ assessments should be performed at Visit 1. In case of the investigator discretion the activities could be speared between visit 1 and visit 2 following the Table 4. Schedule of event

✓ Obtaining the informed consent:

The patient will receive verbal information concerning the aims and methods of the study, its constraints and risks, and the study duration. Written information will be provided to the subjects. Written informed consent must be signed by the patient and Investigator or delegate prior to any investigations

Written informed consent must be obtained prior to any additional corresponding sample collections/ assessments for the optional pharmacogenetic, antibody and other research samples;

- ✓ Assessment of all inclusion/exclusion criteria;
- ✓ Collection of demographic data (age, gender, race, and ethnicity; as allowed per local regulations);
- ✓ Collection of contact information (address, email, home, and cell phone number) for patient, patient's family, if applicable;
- ✓ Complete medical history will be obtained by interview of subjects prior to the first study vaccination to assure eligibility;
- ✓ For WOCBP, contraceptive measures will be reviewed;
- ✓ Measurement of body height and weight;
- ✓ Vital signs, including body temperature and pulse, will be obtained prior to the first study vaccination. Subjects must not eat or drink anything hot or cold, or smoke within 10 minutes prior to taking body temperature.
- ✓ Standard physical examination (PE) will be performed on day 0 prior to the first study vaccination. If subject's medical history is known based on medical records (but not if there are no medical records available at all), a limited, targeted physical examination may be performed instead of standard scope PE prior to the first study vaccination by a study clinician, however in any case neurologic component of PE and physical examination of head/upper respiratory tract must be performed. Except for neurologic, head, and upper respiratory tract physical examination, for other body systems only findings relevant from the study perspective and not obvious from medical history need to be recorded in the eCRF;
- ✓ EDC to be completed (for allocation of patient ID, registration of Screening);
- ✓ All concomitant medications taken before signing the ICF (at minimum those taken within 3 months prior to it, if applicable) will be recorded on the appropriate data collection form prior to the first study vaccination;
- ✓ The following laboratory testing: Urine pregnancy testing for WOCBP;
- ✓ Pre-administration reactogenicity assessments will be performed prior to the first study vaccination to establish baseline. Subjects will then receive a single dose of study vaccine via IM injection in the deltoid muscle of the non-dominant arm. The site of injection (right or left arm) and time of administration will be recorded on the appropriate data collection form. Subjects will be observed in the clinic for at least 30 minutes after the first study vaccination. The study

vaccination site will be examined, and observed reactions, AEs, SAEs (as applicable) will be assessed and recorded on the appropriate data collection form prior to discharge from the clinic.

- ✓ Subjects will be provided with a memory aid (paper diaries) and other study-related materials to record daily body temperature, solicited injection site and systemic reactions, any unsolicited AEs, and concomitant medications. Subjects will be encouraged to take their temperature on the vaccination day in the evening and then at selected approximately the same time each day for next 21/28 days after the vaccination day. Subjects will be instructed on how to complete the contact card in 0-21/28 days, prior to discharge from the clinic. Subjects will be instructed to notify the study center if they develop any reactions after the first study vaccination. PI or appropriate SI will assess the reaction and will give the subject further instructions on the proper course of action, including request for return to the clinic for immediate evaluation. The subjects will be instructed to return the completed contact card in 21/28 days.

